### **1.2 Procedures for HD-tDCS+CILT Sub-study**

After obtaining informed consent, a baseline language assessment will be performed twice, on separate days, for all subjects, regardless of whether they will be assigned to sham or real HD-tDCS stimulation first. The assessment will include some of the previously listed tests, LTROG, Pyramids & Palm Trees, Word Reading, Sentence Writing, and Sentence Repetition. The Western Aphasia Battery will also be administered. The *Western Aphasia Battery* (WAB: Shewan & Kertesz, 1980) samples a number of different language functions and generates a summary score between 0-100 (Aphasia Quotient, AQ), interpretable as general aphasia severity. They will also be given a 60-item screening/probe image set with 4 categories of picture-naming difficulty. There are, from easiest to most difficult: 1) High Frequency Objects, 2) Low Frequency Objects, 3) High Frequency Actions, and 4) Low Frequency Actions. Participants must perform at a rate of at least 50% picture-naming accuracy in the easiest category (High Frequency Objects) at *both* baseline assessments in order to be enrolled in the study. This is because we will start the therapy at the easiest category where we observed 50% accuracy in naming performance; if participants do not reach this level of accuracy in the easiest category of images, they may be too impaired to participate in the therapy without the therapy itself eliciting undue frustration, fatigue, etc. Subjects will also receive the Communicative Activity Log (CAL; Pulvermuller et al., 2001), which assesses the degree to which patients engage in spontaneous communicative behaviors in their day-to-day life. The items will

address speech output and language comprehension. We will also administer a pen-and-paper version of the CAL to participants' primary caregiver (spouse or family member as relevant) at each time-point. Subjects will undergo this combination of assessments on 9 different study visits, as outlined in the study schedule below. This total of nine assessment visits involves two additional assessment visits compared to the tDCS only (i.e., no therapy) study, due to the addition of two, separate, pre-tDCS baseline assessments.

Visits 1 and 2	Visit 3	Visits 4-11	Visit 12		Visit 13	
Baseline language testing and screening	Baseline language testing; Begin HD-tDCS+CI LT	HD-tDCS+CI LT	HD-tDCS+CI LT; Post-HD-tDCS language testing	(6 week break)	Post-HD-tDCS language testing	(6 week break)

Visit 14	Visits 15-22	Visit 23		Visit 24		Visit 25
Post-HD-tDCS/2nd baseline language testing; Begin HD-tDCS+CI LT	HD-tDCS+CI LT	HD-tDCS+CI LT; Post-tDCS language testing	(6 week break)	Post-HD-tDCS language testing	(6 week break)	Post-HD-tDCS language testing

The HD-tDCS stimulation parameters will be similar to the tDCS-only study. 0.5 cm^2 cup electrodes filled with conductive gel will be placed so that the one electrode (anode) is placed over the targeted region of cortex and electrodes of opposite polarity (cathode) are arranged in four equidistant points around the anode to form an imaginary square. Stimulation will not exceed 1.5 mA in intensity and will not exceed 20 minutes in duration per session. As above, 30-second ramp-up and ramp down periods will be employed before and after stimulation for both real and sham sessions. Afterward CI LT, the tDCS electrodes and elastic band or cap will be removed and the subjects' head will be wiped clean. PPA is typically associated with cortical atrophy in the left hemisphere, but the exact location depends on the variant of the disorder. Patients with semantic-variant PPA tend to have atrophy concentrated in the left temporal lobe, whereas patients with nonfluent forms of the disorder tend to have atrophy more concentrated in the left frontal lobe. We will use Soterix tDCS-Explore™ (Soterix Medical Inc., New York, NY) modeling software to place the anode and the cathode over regions that best concentrate the delivery of current to the relevant portion of the left hemisphere. Similar modeling software will be used to determine the exact location of stimulation during HD-tDCS. Based on modeling studies, the current flow during HD-tDCS stays focal, instead of diffusing widely throughout the brain. Exact electrode placement for scalp electrodes presents no additional safety concerns relative to our previous placement of electrodes.

Half of subjects will undergo 10 sessions of sham stimulation first and will then undergo 10 sessions of real tDCS stimulation. Half of subjects will undergo 10 sessions of real tDCS stimulation first and will then undergo 10 sessions of sham stimulation. A complete language assessment will be performed before stimulation sessions, after the 10th stimulation session, and 6 and 12 weeks ( $\pm 1$  week) after the completion of stimulation sessions.

For each HD-tDCS+CILT session, participants will be set up for HD-tDCS (or sham) administration as described above. We will begin stimulation, and once we ensure the participant is comfortable we will begin the CILT session as soon after the start of stimulation as possible. During CILT, the participant will sit at a table across from the researcher. Both the participant and the researcher will have identical sets of cards. The participant will be required to use language to request a card from the researcher to match a card in their set. The participant must describe the content of the card, using only language, to a level of detail that matches a pre-established difficulty criterion for requesting each card. The researcher will give an example of the desired request at the start of each stage of difficulty. The difficulty of the required request will be scaled to individual participants' skill level depending on performance at screening, and on improvement over the course of the study. For example, if a participant's screening indicates they should begin at the level of basic picture-naming, then at first, participants may ask for a card using one word only (e.g., "elephant"). Contingent on performance, the participant will be asked to make more complex requests (e.g., "Do you have elephant?"). Some participants may start at this level, while participants who are less impaired at baseline may start out at a more advanced level. The goal of the therapy for all participants will be to advance in difficulty level over the course of the treatment; for participants of different abilities, the end points of treatment may be different (e.g., some participants may advance to sentence-level requests, while others may only achieve basic phrase-level requests). To avoid fatigue and frustration, the difficulty of the objects on the cards will also be scaled during real-time participant performance. Correct performance on 8/10 items will result in a difficulty increase within each HD-tDCS+CILT session (e.g., increasing the complexity of the request from "elephant" to "do you have elephant?"). If the participant cannot provide a spontaneous object name, they will be provided a hierarchical series of cues for each object to assist naming. They will be given first a semantic cue (e.g., "it's an animal"), then a phonetic cue (e.g., "the first sound is EL"), then a repetition cue (e.g., "elephant" [participant repeats]). Incorrect performance on 5/10 items will result in a difficulty decrease within the session. If participants progress to the maximum difficulty level for a given category of stimuli (i.e., sentence-level requests), the stimuli used at the next HD-

tDCS+CILT session will be from a more difficult category (e.g., moving from high to low frequency objects, or from low frequency objects to high frequency actions, and so on). Sessions will be audio-recorded and performance will be scored across cuing levels. The CILT sessions will last up to 1.5 hours each, with HD-tDCS terminating after 20 minutes of stimulation.

Safety and tolerability of the treatment will be assessed in several manners. First, the inclusion/exclusion screening form will be administered both at the initial intake session, as well as at the first session of each 2-week stimulation block. Second, subjects will be queried about new symptoms or adverse effects prior to stimulation on all days when stimulation will be given; should subjects have any concerns, HD-tDCS will not be performed and language will be assessed with fluency tests, naming and a speech sample will be elicited. Third, language will be assessed immediately following the 10th HD-tDCS+CILT session with the WAB, the 60-item image set, and the patient/caregiver CAL. Should there be a clinically significant decrease in performance on the WAB (a reduction in score of **5 or more points**) compared to the participant's WAB score on day 1 of the treatment, the participant's visits will be discontinued; in this event, subjects will be followed on a weekly basis for 4 weeks or until performance returns to baseline (whichever comes first). We propose to use a "significant" change in performance as a cut-off because performance in this condition in the absence of any intervention is quite variable.

After the final visit of the HD-tDCS+CILT sub-study (i.e., the last 12-week follow-up), participants will have the option to participate in one additional round of 10 HD-tDCS+CILT sessions, to be scheduled no earlier than 3 months after study completion and no later than 6 months following study completion.

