**PROTOCOL ABSTRACT**

The purpose of this study is to treat the language impairment of subjects with Primary Progressive Aphasia using transcranial direct current stimulation (tDCS) and high definition transcranial direct current stimulation (HD-tDCS). PPA is a slowly progressive impairment in language that may be observed in patients with neurodegenerative conditions such as Fronto-temporal dementia or, less commonly, Alzheimer's Disease. tDCS is a form of non-invasive brain stimulation in which very small current (here, 1.5 mA) is applied to the scalp. tDCS will be administered in ten 20 minute sessions over the course of two weeks. Language function will be assessed before, after 1 week of treatment, after 2 weeks of treatment and at 6 and 12 weeks after completion of tDCS. In a sub-study under this protocol, we will pair HD-tDCS with Constraint-Induced Language Therapy (CILT), which preliminary evidence has shown may be a useful speech therapy for individuals with PPA. In this sub-study, we will investigate whether HD-tDCS can enhance the potential benefits of speech therapy (usually very modest in PPA).

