### **1.2 HD-tDCS+CILT Sub-study Objectives**

The objective of the HD-tDCS+CILT sub-study is to improve language function in patients with Primary Progressive Aphasia using a combination of HD-tDCS and a form of intensive speech therapy called Constraint-Induced Language Therapy. The HD-tDCS+CILT sub-study shares many of the design features of the tDCS-Only study in 1.1, therefore, we will include additional information about HD-tDCS+CILT in its own section where relevant to help delineate the differences between these two studies. Any sections that do not include a HD-tDCS+CILT sub-section apply identically to both studies.

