## ***8. Real time safety monitoring***

Subjects and equipment will be monitored at all times during tDCS and HD-tDCS studies by a trained member of the research personnel list approved to be on the protocol. During the first stimulation session, participants will come to the lab here at the University of Pennsylvania and a physician will be on call within 5 minutes of the testing room. As long as the subject does not experience any adverse events during that first stimulation session and the research staff have no

reservations, then in all subsequent stimulation sessions, whether conducted in the patient's home or in the laboratory here at the University of Pennsylvania, one of the physicians associated with the study will respond to any concerns within 24 hours. Additionally, the trained personnel administering stimulation will look for any evidence of discomfort in the participant and will verbally inquire about any discomfort. The investigator or trained personnel will also observe and monitor the equipment. In the unlikely event that either the subject or the person administering tDCS or HD-tDCS has significant concerns and the PI cannot be immediately contacted, the subject would be escorted to the Emergency Room.

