#### ***2.2 Design for HD-tDCS+CILT Sub-study***

For the HD-tDCS+CILT study, we will use the same sham-controlled, full cross-over design described above, with two exceptions: 1) We will conduct two baseline testing sessions on separate days prior to the start of the 10-day tDCS block, to facilitate screening for CILT and to ensure a stable estimate of language performance at baseline; 2) After the completion of the final 12-week follow-up visit, participants will have the option to undergo an additional 10-day round of “booster” HD-tDCS/sham+CILT. This booster will be open to any patients as an optional incentive for patients whose completion of the study coincided with perceived benefits from the combined therapy. The booster will involve the same time-course of language assessments, HD-tDCS+CILT sessions, and follow-up testing out to 12 weeks after the final HD-tDCS session. This optional third arm of the protocol will thus be identical to the real HD-tDCS arm in all ways (i.e., assessment schedule, subject compensation, tDCS parameters etc.) except that participants may opt in or out as they see fit. In other words, all participants are expected to complete the first two arms of HD-tDCS/sham stimulation; then, those who have completed all the scheduled study visits may choose to undergo a third round, during which we will continue to collect the same data that we have collected throughout the rest of the study.

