### **3.2 Study Duration of HD-tDCS+CILT Sub-study**

We expect this project to last for approximately 2 years. We expect to enroll approximately 10 subjects annually. Duration of subjects' participation in the study will be approximately 8-16 months, depending on the participants' choice to undergo booster therapy or not.

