## **STUDY PROCEDURES**

### **1.1 Procedures for tDCS-Only Study**

After obtaining informed consent, a baseline language assessment will be performed for all subjects, regardless of whether they will be assigned to sham or real tDCS stimulation first. Depending on the subject, this assessment is expected to take 1-2 hours. Performance will be audio-recorded. The assessment will include the following measures: - Confrontation Naming: we will administer the Boston Naming Test, a commonly used measure of picture naming/word retrieval in which a line drawing is presented and subjects are asked to name the object. - Pyramid and Palm trees: a well-standardized test in which subjects see 3 pictures or words on a page and are asked which two "go together"; for example on one page, the pictures include a drawing of a glove, hand and foot. -Grammatical Comprehension (L-TROG): a standardized test in which subjects are asked to judge whether an auditorily presented sentence is correct. - Category fluency: a series of tasks in which subjects are asked to generate as many words as possible in one minute that are

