
stimulation.

Safety and tolerability of the treatment will be assessed in several manners. First, the inclusion/exclusion screening form will be administered both at the initial intake session, as well as at the first session of each 2-week stimulation block. Second, subjects will be queried about new symptoms or adverse effects prior to stimulation on all days when stimulation will be given; should subjects have any concerns, tDCS will not be performed and language will be assessed with fluency tests, naming and a speech sample will be elicited. Third, in the absence of symptoms, language will be assessed at the end of one week of treatment with picture naming, fluency measures and a speech sample will be elicited. Should performance be significantly worse than prior to initiation of treatment, the study will be discontinued; in this event, subjects will be followed on a weekly basis for 4 weeks or until performance returns to baseline (whichever comes first). We propose to use a "significant" change in performance as a cut-off because performance in this condition in the absence of any intervention is quite variable.

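### HD-tDCS+CILT: the only scheduled language check with a stopping threshold comes after session 10, so it cannot shorten the block in which a decline occurs (minor; a week-1 check is a cheap improvement)

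*Combined protocol and SAP*

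**What the plan says.** Study Procedures, 1.2 (combined protocol and SAP) lists three safety steps for HD-tDCS+CILT. The first two are repeat screening at intake and at the start of each block, and a symptom query before every stimulation day. The third begins "Third, language will be assessed immediately following the 10" and refers to the 10th session. It uses the WAB, the 60-item picture set and the communication log. If the WAB is 5 points or more below day 1, the participant's visits end and weekly follow-up begins.

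The other two components place their third step earlier. Study Procedures, 1.1 (tDCS-only) states that "language will be assessed at the end of one week of treatment with picture naming", together with fluency and a speech sample, when no symptoms have been reported. A participant who is significantly worse is discontinued. Study Procedures, 1.3 (svPPA) uses the same wording. Neither defines significantly worse.

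The Protocol Abstract says in general terms: "Language function will be assessed before, after 1 week of treatment, after 2 weeks of treatment". Objectives, 1.2 adds: "Any sections that do not include a HD-tDCS+CILT sub-section apply identically to both studies".

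**The concern.** A participant in HD-tDCS+CILT whose language falls in the first week of active stimulation, and who raises no concern, is scheduled for all 10 sessions before any threshold is applied. In the other two components the same participant would be tested about halfway. Section 1.2 keeps their first two safety steps but moves the third to the end of the block, and gives no reason.

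The stake is exposure to the remaining sessions of one block. The efficacy comparison is not directly affected.

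**Working it through.** **1. Reproduce the plan's count of assessment visits.** Section 1.2 states nine. Its table shows language testing at visits 1, 2, 3, 12, 13, 14, 23, 24 and 25, which is nine. The section also says this is two more than in tDCS-only. That component has baseline, post, 6 weeks, 12 weeks (also the second baseline), post, 6 weeks and 12 weeks, which is 7, and 7 + 2 = 9. Both figures reproduce.

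**2. Locate the sessions.** Block 1 is visits 3 to 12, so session k is visit k + 2. Block 2 is visits 14 to 23, so session k is visit k + 13. Each has 10 sessions. No assessment visit falls in 4 to 11 or in 15 to 22.

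**3. Sessions that a check can avert.** The ceiling is 10 minus the sessions already given.
- Present rule: 10 − 10 = 0, in either sequence.
- Check before session 6 (visits 8 and 19), assuming five sessions a week: 10 − 5 = 5. If week 1 holds 4 or 6 sessions, the ceiling is 6 or 4.
- Five sessions are at most 5 × 20 = 100 minutes of stimulation and 5 × 1.5 = 7.5 hours of CILT.

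This is a ceiling because the decline must be present by session 6, be detected and be confirmed. A later decline averts nothing. The documents give no basis for an expected value.

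**4. Does other text already supply the check?** The abstract has no separate HD-tDCS+CILT part, so its week-1 assessment could be read to cover the sub-study. It states no threshold and no action. Section 1.2 is the specific text, and it schedules full assessments only before the sessions, after the 10th, and at 6 and 12 weeks.

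**5. Should the WAB rule simply be repeated at week 1 for everyone?** The documents give no SD of WAB change, so a range is assumed. With no true change and normal errors, one look trips falsely with probability p = Φ(−5/SD). Over two blocks with the session-10 look only, the risk is 1 − (1 − p)². Adding a week-1 look that shares the day-1 score was simulated.

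| Assumed SD of change | p per look | Two blocks, session 10 only | Two blocks, week-1 look added |
|---|---|---|---|
| 2 | 0.006 | 1% | 2% |
| 4 | 0.106 | 20% | 32% |
| 6 | 0.202 | 36% | 53% |

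If the WAB is noisy, repeating it for everyone adds appreciable false stops. Giving it only after a clear fall on a short test cannot add more than this and should add fewer.

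**6. Should the margin be scaled to each participant's own baseline variation?** Visits 1 to 3 give three values and so 2 degrees of freedom. The 95% range of the estimated SD is √(χ²/2), from √(0.0506/2) = 0.16 to √(7.378/2) = 1.92 times the true SD, which is too unstable for a stopping margin. Visit 3 is also session 1 of block 1. The repeated baseline, included "to ensure a stable estimate of language performance at baseline", serves its stated purpose but does not support an individual SD.

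**The case against.** The best defence is that this is a design choice and that observation in this sub-study is arguably closer than in the others. Participants do up to 1.5 hours of structured language work at every session, scored by cue level, with difficulty lowered after 5 errors in 10. Before each stimulation day they are asked about symptoms, and a concern withholds stimulation and triggers language testing. Under Characteristics of the Study Population, section 8, "the trained personnel administering stimulation will look for any evidence of discomfort in the participant", and the person giving stimulation can act on a concern of their own. A physician responds within 24 hours. The other components' week-1 criterion is undefined, whereas this sub-study has a number. HD-tDCS is described as minimal risk.

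Most of this stands and keeps the point minor. It does not close the gap, because none of these safeguards has a decline threshold. The query depends on self-report, in a population some of whom are expected to have difficulty understanding. Staff are told to look for discomfort, which need not accompany language loss. CILT difficulty adapts to performance, so raw session scores are not comparable over time.

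A reader might infer that participants are unmonitored within the block, that stimulation is known to worsen language, or that the session-10 rule has no use. The documents support none of these. Monitoring exists, as listed above. No evidence of decline within a block is given. The end-of-block rule stops later visits, starts follow-up, and after a decline on sham can cancel the active block in sham-first participants.

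**Conclusion.** The point holds as a minor, cheap safety improvement. The threshold check averts 0 of 10 sessions in the block where the decline occurs. A check at about session 6 raises the ceiling to about 5 of 10 (4 to 6, depending on how many sessions fall in week 1). These figures follow from the visit table and an assumed five sessions a week. The expected benefit, the false-hold rate and the number of extra false stops cannot be derived from the documents. They depend on the margin chosen and on naming and WAB variability, which are not given. The abstract suggests that the missing week-1 visit may be an omission from section 1.2. In that case the change brings the section into line with the rest of the protocol.

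**What to change.** Add to Study Procedures, 1.2 and the visit table, in both arms, both blocks and any booster block:
- **Test.** Before stimulation at about session 6 (visits 8 and 19), give the 60-item naming set, which is already given at baseline and on day 1 and can be scored on the spot. Verbal fluency is optional, and only if also added on day 1 of each block, because section 1.2's listed battery names no fluency test. Section 1.1 describes category fluency as "a series of tasks in which subjects are asked to generate as many words as possible in one minute". Three categories and three letters, at an assumed one minute per letter, take about 6 minutes.
- **Action.** If the score is below that block's day 1 by one margin fixed in advance for all participants, hold stimulation, give the WAB and apply the existing 5-point rule before any further session.
- **Speech sample.** It may be recorded but should not decide whether stimulation goes ahead that day, because Study Procedures, 1.1 has speech scored off-line.
- **Keep** the end-of-block check.

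Cost: an amendment to the section 1.2 text and table, with no new visit and no new instrument. Study Design, 3.2 says "We expect to enroll approximately 10 subjects annually" for about 2 years, so about 20 participants × 2 blocks = 40 short checks, or 60 if all take the booster. At $25 an hour, even a full hour per check would cost 40 × 25 = $1,000 (60 × 25 = $1,500) in payments. There is slight extra test exposure, equal in both arms. There will be some false holds, each costing one WAB, and a small number of extra false stops. Declines outside the tested abilities, or after session 6, would still wait for session 10.

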[name], Vyas, & Olson, 2013). tDCS has been used in the treatment of patients with neurodegenerative diseases (e.g., Benninger et al., 2010; Boggio et al., 2012; Hansen, 2012). We are aware of only one report in which tDCS was administered to a subject with PPA; there was significant improvement in some language functions in the absence of adverse effects (Wang, Wu, Chen, Yuan, & Zhang, 2013). HD-tDCS is an emerging technique of noninvasive brain stimulation that has been tested in a limited number of aphasic populations with comparable effects to traditional tDCS (Sebastian, Tsapkini & Tippett, 2016; Richardson et al., 2015). This new type of stimulation will provide a more focal flow of current than traditional tDCS. Primary progressive aphasia (PPA) is a behavioral disturbance characterized by the insidious onset and slow progression of language impairments in the context of a neurodegenerative disease. In different patients, the deficits may differentially impact comprehension, semantics or verbal fluency. Autopsy studies demonstrate that most patients with PPA suffer from Fronto-temporal dementia but Alzheimer's Disease, Dementia with Lewy Bodies and cortico-basal ganglionic degeneration may also cause the disorder. The disorder leads to a profound impairment in language and, ultimately, to a generalized severe dementia involving all domains of cognition. CILT is an intensive language therapy protocol, first developed by Pulvermuller and colleagues (2001) for use in language rehabilitation following stroke. The central principles of CILT are massed practice over many hours, combined with restricting communication to use of verbal language only (i.e., no gestures or other communication). Throughout the course of a CILT treatment, the difficulty of each stage of therapy is also scaled to individual patient performance, such that patients' language abilities can be sequentially behaviorally "shaped" to ensure a low rate of failure and a gradual increase of difficulty as improvements are made and new skills are retained. Traditional speech therapies are not typically as beneficial for individuals with PPA relative to individuals with post-stroke aphasia due to the progressive nature of the disorder. However, because the central principles of CILT involve massed practice over many hours, paired with constraining communication to the use of language, CILT may thus be useful in the *retention* of language in PPA in addition to aiding in the reacquisition of language after stroke. A recent study has shown modest benefits of an intensive CILT protocol in two individuals with PPA (Hameister et al., 2016), but further questions remain regarding how effective CILT may be for PPA and how long patients can expect the benefits of CILT to last.

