## **2. Statistical Analysis**

Data from each subject will be analyzed using a within-subject design in which change in performance from the baseline testing session to the post-therapy (0, 6, 12 weeks post tDCS) will be compared using t-tests, ANOVAs and other univariate statistics. As it is most relevant to real-world behavior, elicited speech production will serve as the primary endpoint. Depending on our ability to recruit a reasonable sample, group analyses will be also be performed. Finally, we note that high quality imaging will be available for the majority of subjects. Note that we are not proposing to obtain imaging under the auspices of the present study; this data will be available from [name] previously cited protocol. We will perform exploratory analyses in which we attempt to determine if specific imaging parameters (e.g., cortical thickness, degree of atrophy) predict response to tDCS.

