### ***2.2 Potential Study Benefits of HD-tDCS+CILT Sub-study***

The study is being performed to determine if HD-tDCS in combination with CILT improves subjects' language performance. The potential benefit of the study to the subjects, therefore, is that they will improve with respect to language function. This may occur during CILT+sham, CILT+HD-tDCS, or both. The study will also be of benefit to the community of physicians and clinicians attempting to treat PPA.

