**6. Risk/Benefit Assessment**

The risks as well as the potential benefit of the study are modest. tDCS has been delivered to subjects with primary degenerative diseases of the brain in multiple studies without adverse effects. The benefits, however, are also expected to be modest. The treatment may improve language function but in the setting of a primary degenerative condition, the benefit is likely to be modest. There is no reason to believe that the treatment will modify the underlying course of the disease.

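### HD-tDCS+CILT: the 5-point WAB rule, read naturally, cancels the 6- and 12-week assessments of participants who declined, so a group mean change from baseline at those visits will tend to look too good within each condition

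*Combined protocol and SAP*

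**What the plan says.** Section 1.2 of Study Procedures (HD-tDCS+CILT) repeats the WAB right after the 10th session of a block. The comparison is with the participant's "WAB score on day 1 of the treatment". If the score is 5 or more points lower, the participant's "visits will be discontinued; in this event, subjects will be followed on a weekly basis for 4 weeks" or until performance is back at baseline, whichever is sooner. The section gives no rule for resuming the schedule.

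The same section plans the late assessments without naming any exception: "A complete language assessment will be performed before stimulation sessions, after the 10th stimulation session, and 6 and 12 weeks" after stimulation. It also counts assessments as visits: "Subjects will undergo this combination of assessments on 9 different study visits". In its visit table, the only visits after the end of block 2 (Visit 23) are Visits 24 and 25, and both are language testing.

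Study Procedures, 2. Statistical Analysis, says that "change in performance from the baseline testing session to the post-therapy (0, 6, 12 weeks post tDCS) will be compared using t-tests, ANOVAs", among similar one-variable methods. Group analyses depend on recruiting a reasonable sample. Missing data are not mentioned. The Background lists as an open question "how long patients can expect the benefits of CILT to last".

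**The concern.** When the rule is applied, the block's ten sessions are finished, so there is no treatment left in that block to stop. What remains is the block's two late assessments and, after block 1, the second block. The weekly follow-up lasts at most 4 weeks. It ends before the 6-week assessment, even at the early edge of its 1-week window.

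If the rule cancels these visits, whether a participant has 6- and 12-week data depends on how that participant scored at week 0. Those who declined are removed, and the late mean is taken over the others. Where immediate and late change are positively correlated, that mean is too high as an estimate of change from baseline. This touches the Background's question of how long benefit lasts. With about 20 participants expected (about 10 a year for about 2 years, Study Design 3.2), each lost visit also costs precision.

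**Working it through.** The plan has no figure of its own to reproduce, so this is an illustration on stated assumptions.

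**Inputs from the documents.** Threshold: a fall of 5 points. Participants: about 20. Late assessments: 2 per block over 2 blocks, so 20 × 4 = 80 scheduled.

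**Assumptions.** WAB change at the end of a block is normal with mean m and SD s from 3 to 6, with the same SD at 12 weeks. The correlation r between 0- and 12-week change is 0.5. Blocks are independent, and the reference is day 1 of each block. A mean above 0 is plausible in either condition, since the protocol says of improvement: "This may occur during CILT+sham, CILT+HD-tDCS, or both". A mean below 0 is also plausible in a progressive disease: "There is no reason to believe that the treatment will modify the underlying course of the disease".

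**Step 1: chance of a trigger per block.** With a = (−5 − m)/s, P = Φ(a). At m = 0 and s = 5, a = −1 and P = 15.9%.

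**Step 2: excess in the 12-week mean change from baseline among those remaining.** Excess = r × s × φ(a)/(1 − Φ(a)). At m = 0 and s = 5: 0.5 × 5 × 0.2420/0.8413 = 0.72.

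| | SD 3 | SD 4 | SD 5 | SD 6 |
|---|---|---|---|---|
| Trigger, m = 0 | 4.8% | 10.6% | 15.9% | 20.2% |
| Trigger, m = +3 | 0.4% | 2.3% | 5.5% | 9.1% |
| Excess, m = 0 | 0.16 | 0.41 | 0.72 | 1.06 |
| Excess, m = +2 | 0.04 | 0.18 | 0.41 | 0.69 |
| Excess, m = +3 | 0.02 | 0.11 | 0.29 | 0.54 |

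At m = 0, r = 0.3 gives 0.1 to 0.6, r = 0.7 gives 0.2 to 1.5, and r = 0 gives none. For scale, the standard error of a 20-person mean is s/√20, or 0.7 to 1.3. A separate simulation with measurement error and a true 12-week change of −2.0 showed −1.86 to −0.53 among those remaining, so the shift was upward in all 12 scenarios.

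**Step 3: active minus sham at 12 weeks.** With equal means and SDs the two excesses cancel. With sham 0 and active +3, subtract the rows: 0.02 − 0.16 = −0.14, then −0.30, −0.43 and −0.52. The shift is against active.

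**Step 4: change from week 0 to week 12 among those remaining.** The shift is (r − 1) × s × φ(a)/(1 − Φ(a)). At m = 0 and r = 0.5 it is −0.16, −0.41, −0.72 and −1.06, so the sign reverses. The measurement-error simulation agrees: −2.1 to −3.2 against a true −2.0.

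**Step 5: assessments lost.** With trigger chances p1 and p2 in blocks 1 and 2, the expected loss per participant is 4·p1 + 2·(1 − p1)·p2. At SD 5, sham 0 and active +3:
- Sham first: 4 × 0.1587 + 2 × 0.8413 × 0.0548 = 0.727.
- Active first: 4 × 0.0548 + 2 × 0.9452 × 0.1587 = 0.519.
- The average, 0.623, times 20 is 12.5 of 80.

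Across SD 3 to 6, with a 3-point benefit, the loss is 3 to 17 of 80 if the sham mean is 0, 1 to 10 if it is +2, and 11 to 26 if it is −2. With sham 0, between 0.5 and 2.9 of 20 participants also lose block 2.

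**The case against.** - **Cancellation is inferred.** The rule does not name the 6- and 12-week assessments, and the sentence that schedules them has no exception. The visit table also numbers treatment sessions as visits. After block 2 there is still an optional booster round that the rule could stop, so it would not be empty even if Visits 24 and 25 were kept. All of this stands: a reader might infer that the protocol expressly cancels the late assessments, and it does not. Cancellation remains the natural reading, because the scheduled visits are what is said to stop and a shorter follow-up replaces them. If the other reading is meant, the text still leaves staff to decide.
- **Direction.** A reader might infer that durability in every sense will look better. The documents do not support that. The upward shift belongs to change from baseline within a condition, which is the contrast in the Statistical Analysis section. For the share of the week-0 level kept to week 12, the sign reverses (step 4).
- **Stimulation against sham.** A reader might infer that the rule favours active stimulation. It does not (step 3). The shift of 0.14 to 0.52 against active is 0.15 to 0.27 of a contrast standard error of s × √(2/20), or 0.95 to 1.90.
- **Conditional analysis and choice of outcome.** A group mean arises only if the optional group analysis is done. The figures are for the WAB, on which the rule selects. Bias on naming, the Communicative Activity Log or other measures depends on their unknown correlation with WAB change. Elicited speech, the stated primary endpoint, is not in this sub-study's assessment list, so nothing is claimed about it.

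**Conclusion.** The point holds in a limited form. On the natural reading, the rule makes 6- and 12-week data missing because of an observed decline, and no handling is stated. In a group analysis of change from baseline, the late mean within a condition will tend to be too high. Under the assumptions listed, the excess is about 0.2 to 1.1 WAB points with an immediate mean of 0, and 0.0 to 0.7 with a mean of +2 to +3. It is negligible if the SD is near 3 and mean gains are positive. No claim is made that the active-sham difference is inflated. Confidence is medium, because cancellation is inferred and the SD, mean and correlation are all assumed.

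**What to change.** 1. In Study Procedures 1.2, state that the 5-point criterion stops further stimulation and CILT only, including block 2 and the booster. Participants who meet it keep that block's scheduled 6- and 12-week assessments if willing.
2. In the Statistical Analysis section, state that any group analysis includes all available visits of all randomised participants, not only completers of both blocks. A simple mixed model that includes the immediate post-block WAB would serve.
3. Report the number stopped, by block and sequence.

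This takes about one sentence in each section. The assessments are already scheduled and the safety stop is unchanged. The downside is voluntary testing burden for people who have declined.

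In the same illustration (sham 0, 3-point benefit) with full attendance, only block-2 assessments after a block-1 stop stay lost: 1.0 to 5.9 of 80 instead of 3.1 to 16.9, so about two thirds return. The excess at m = 0 falls from 0.2–1.1 to 0 with independent blocks, or to 0.0–0.2 with a between-block correlation of 0.5. If only half attend (independent blocks), it is 0.1–0.5.
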